1.3.12. Summary of Clinical Studies with GKT137831

Healthy Subjects Program

Four Phase 1 studies were conducted with GKT137831 in order, in part, to characterize the safety and tolerability profile of GKT137831 in healthy male subjects. The studies were designed to examine the safety and pharmacokinetics of single and multiple ascending doses of GKT137831, the potential for drug interactions through the inhibition of CYP3A4 substrate midazolam, as well as the relative bioavailability of micronized and unmicronized GKT137831 and the potential interactions with food.

A total of one hundred and five (105) healthy male subjects received GKT137831 in four Phase 1 studies. All the Phase 1 studies were conducted at a single clinical pharmacology unit located in Paris, France and were all conducted in accordance with the principles of Good Clinical Practice (GCP). Doses administered ranged between 10 mg and 1800 mg. In the multiple dose study, GKT137831 was administered over 10 successive days. The mean age of subjects in all four studies was between 30.0 and 33.6 years (mean) with a range of 18 to 49 years.

In the phase I program, GKT137831 was well tolerated with low incidence of adverse events. There were no deaths, no serious adverse events, and no adverse event of severe intensity. Most were treatment emergent adverse events (TEAEs) and were mild and self-limiting, and were considered not related to treatment by the Investigator. Of the 105 subjects dosed with GKT137831 or matching placebo in the 4 Phase 1 studies, 41 subjects reported adverse events (39%), of which 39 were TEAEs. The most frequently reported TEAEs in subjects receiving GKT137831 were events related to headaches (10 TEAEs i.e. 25.6%). Other TEAEs were non-specific infections unrelated to GKT137831.

There were no vital sign, ECG, hematology, clinical chemistry or urinalysis findings of any clinical significance, as defined by the principal investigator. Thyroid hormones were investigated in the multiple ascending dose study and all mean values were within the normal range and changes compared to baseline showed no trend over time.

The pharmacokinetics of GKT137831 were generally consistent between all four studies. Administration of micronized rather than unmicronized drug substance did not appear to have any notable impact on plasma exposure. Administration with food did have an impact on extent of exposure and/or inter-subject variability.

Exposure to GKT137831, measured by mean AUC and C_{max} , whether after single or repeat administration, increased with increasing dose up to 900 mg in a broadly dose proportional manner (single dose; GSN000108) or less than dose proportional manner (single and repeat dose; GSN000109). No increased exposure was seen upon single administration of doses higher than 900 mg. No reduction in mean exposure was seen upon repeat dosing either at daily doses of 100-900 mg (GSN000109) or twice-daily doses of 300-400 mg (GSN000109, GSN000198). A slight accumulation in AUC_{0-t} was seen between the first and last doses upon twice daily dosing, and this is consistent with the increased dosing frequency compared with once-daily. The mean exposure was comparable between studies. After a single dose of 300 mg (a dose level common to all four studies, and including both micronized and unmicronized drug) in either the fasted state or with a non-high-fat meal, the mean AUC_{0-t} ranged from 24,100 to 38,000 ng.h/mL.

Phase 2 Program

A multi-centre double blind randomized phase 2 study has been conducted to evaluate the efficacy and safety of GKT137831 in the treatment of diabetic kidney disease. A total 136 patients were randomized in the study. In the GKT137831 arm, 68 subjects received 100 mg bid for 6 weeks followed by 200mg bid for a further 6 weeks, representing over 15.22 subject years in GKT137831 exposure.

The trial did not meet its primary efficacy endpoint. At the end of the treatment period, no difference could be detected between GKT137831 and placebo in changes in albuminuria from baseline. GKT137831 did not appear to affect other measures of renal function and injury, including serum creatinine, eGFR, and urine MCP-1. Reasons for the lack of efficacy on the primary endpoint may include the short treatment period and/or underdosing during the first half of the trial.

However, GKT137831 achieved statistically significant reductions in gamma glutamyl transpeptidase (GGT) and high sensitivity C-reactive protein (hs-CRP), two markers which predict mortality in patients with diabetic kidney disease. Furthermore, subjects receiving GKT137831 also showed a robust trend for lower levels of serum amyloid protein A, interleukin-6, and triglyceride levels, compared to subjects receiving placebo. These changes are potentially related to a systemic anti-inflammatory effect, and/or to reduced severity of non-alcoholic fatty liver disease (NAFLD) in these subjects with type 2 diabetes and excess body weight. Trends towards reduced neuropathic pain and erectile dysfunction were also observed but did not reach statistical significance.

In this Phase 2 study, GKT137831 was well tolerated. The reporting rate of AEs was low with less than 50% of subjects reporting at least 1 AE over the course of the study. In GKT137831 treated subjects, the incidence of AEs was significantly lower than in patients receiving placebo. Most treatment-emergent adverse events were self-limiting, mild in severity, not treatment-related and resolved rapidly. The most commonly reported adverse events were events related to respiratory tract infections. Other reported events were single occurrences experienced by 1 or 2 GKT137831

subjects. There was no evidence of dose-related increase in the occurrence of treatment emergent adverse events. The only notable safety finding was a statistically significant, albeit slight and non-clinically significant (~2.5 mm Hg) increase in DBP. A trend for a marginal (~3 mm Hg) increase in SBP was also observed, but did not reach statistical significance. Finally, safety signals related to findings made in toxicology studies were not detected. In particular, there were no safety signals related to thyroid function, liver function, bone marrow function, or cardiac conduction. No bone marrow toxicity, cardiac toxicity, liver toxicity, or renal toxicity was observed.

Upon review of all available safety data, GKT137831 at doses up to 200 mg BID in 68 subjects with diabetic kidney disease indicated a good tolerability and safety profile compared to placebo.

The safety and efficacy of GKT137831 was subsequently evaluated in patients with primary biliary cholangitis (PBC). Several components of the disease were assessed, including liver inflammation and injury, liver fibrosis, cholestasis, autoimmune activation, and important symptoms such as fatigue and itching. The trial was a placebo controlled, double blind, randomized, parallel group trial that included a total of 111 subjects with inadequate response to ursodeoxycholic acid (UDCA). Eligible subjects received GKT137831 400mg OD, 400mg BID, or matching placebo for 24 weeks in addition to continued treatment with a stable dose of UDCA. The primary efficacy endpoint was changes in gamma glutamyl transpeptidase (GGT) at week 24.

The trial was conducted at 62 investigational centers located in North America, Europe, and Israel. Patient enrolment was completed in September 2018 and interim efficacy results were obtained in November 2018. The trial met its primary and secondary interim efficacy endpoints, which included markers of bile duct and liver injury measured after only 6 week of treatment. Importantly, the 400mg bid dose achieved superior efficacy compared to the 400mg od dose. The Safety Monitoring Board overseeing the safety of participating subjects conducted its third data review in October 2018, and recommended that the trial continue as planned. Top line efficacy results after 24 weeks of treatment were communicated on May 2, 2019. GKT137831 continued to induce reductions in the primary efficacy variable GGT over time, although the reduction observed at week 24 did not reach statistical significance. However, a statistically significant reduction in a secondary marker of bile duct injury (alkaline phosphatase) was significantly reduced in patients receiving GKT137831 BID. In addition, GKT137831 achieved a 22% reduction in liver stiffness (a non-invasive measure of liver fibrosis), compared to a 4% increase in liver stiffness for placebo ($p<0.05$). Furthermore, GKT137831 achieved robust reductions in pruritus, a major symptom affecting the quality of life of PBC patients. These results indicate GKT137831 has anti-inflammatory and anti-fibrotic properties in PBC patients. Importantly, GKT137831 continued to be very well tolerated over the full 24-week treatment period. Only 2 serious adverse events (SAEs) were reported. These included a case of multiple bone fractures related to a traffic accident, and a case of grade 1 urinary tract infection (the event was deemed serious because the patient was hospitalized to initiate IV antibiotic therapy). These 2 SAEs were believed to be unrelated to the study drug. Both patients completed the full treatment period without interruption of study drug administration. Over 93% of patients completed the full treatment period.

The good safety profile of the two doses tested, and the superior efficacy of the 400mg bid dose support the selection of the 400mg bid for this trial in IPF patients.

GKT137831 is currently being evaluated in an investigator-initiated trial assessing the effect of this drug on markers of kidney injury and function. The trial is a placebo controlled, double blind, randomized, parallel group trial that includes a total of 142 subjects with type 1 diabetes and micro-albuminuria despite receiving standard of care therapy. Eligible subjects receive GKT137831 200mg BID or matching placebo for 48 weeks. The primary efficacy endpoint is change in urinary albumin to creatinine ration (UACR) at week 48. The trial is being conducted at approximately 15 investigational centers located in Australia. The trial was initiated in January

2018. The study is blinded and patient enrollment is at an early stage. Following the interim and final efficacy results obtained in the PBC trial, it is planned to increase the GKT137831 dose to 400mg bid. This efficacy data also indicates GKT137831 was underdosed in the first clinical trial in patients with diabetic kidney disease.

1.4 SIGNIFICANCE

If our hypothesis is correct, treatments that reduce ROS generation and consequent injury will have beneficial effects in IPF patients. The proposed clinical trial here will generate important preliminary data regarding the magnitude and duration of GKT137831 effects in IPF patients. These data will be essential for design of a subsequent clinical efficacy (Phase III) study.

2 RESEARCH DESIGN AND METHODS

2.1 CLASSIFICATION AND METHODOLOGICAL DESIGN

This is a multi-center, randomized, double-blind, placebo-controlled Phase II clinical trial to examine selected effects and safety of GKT137831 in IPF patients.

2.2 STUDY DESIGN

Participants will be recruited from among the ambulatory IPF patient populations at the collaborating institutions.

Following completion of screening and eligibility assessments, 60 IPF patients will be randomly assigned to one of two cohorts intended to receive either GKT137831 or matching placebo, in a ratio of 1:1 (i.e., n = 30 in each arm). Both GKT137831 and placebo will be administered by mouth (p.o.), twice daily (b.i.d.). Each GKT137831 capsule will contain 100 mg of the active drug. Drug (and placebo) will be administered for 24 weeks. Each participant will also be surveyed by phone interview at week 28 (one month after completion of drug administration).

All participants will have physiological assessments that are standard of care for IPF patients, including high resolution chest CT scans (HRCT scans), and pulmonary function tests (spirometry, diffusion capacity, 6-minute walk distance) prior to and after the conclusion of therapy. These procedures and routine laboratory tests will not be repeated specifically for this study if they are deemed to be clinically indicated. The results of any standard-of-care procedures will be extracted from the participant's medical record and used as research data.

Patients will be monitored carefully for occurrences of adverse events. Adverse experiences will be evaluated according to criteria outlined in the NCI Common Terminology Criteria for Adverse Events (CTCAE), version 5.0.

Patients removed from treatment due to unacceptable adverse events will be followed for a total of 24 weeks under the principle of intent to treat.

2.3 INCLUSION AND EXCLUSION CRITERIA

Potential participants will be identified by attending physicians (i.e., collaborating center Co-Investigators or their designees). Subjects who sign informed consent will be assigned a deidentified study ID and will be screened for inclusion and exclusion criteria.

Inclusion Criteria

- 1) Age between 40-85 years old.
- 2) A diagnosis of IPF that fulfills current ATS/ERS Consensus Criteria (1).
- 3) IPF duration <5 years, based on the date of definitive diagnosis.
- 4) Ability and willingness to give informed consent and adhere to study requirements.
- 5) Ratio of forced expiratory volume in 1 second to forced vital capacity (FEV₁/FVC) >70% of predicted values.

Exclusion Criteria

- 1) Diagnosis of major comorbidities expected to interfere with study participation
- 2) History of malignancy, excluding basal or squamous cell skin cancer and low-risk prostate cancer, the latter defined as stage T1 or T2a, with prostate specific antigen <10 ng/dL. NOX inhibition is not known to promote cancer, and these criteria are within current guidelines.
- 3) The occurrence of any acute infection requiring systemic antibiotic therapy within 2 weeks prior to Screening (Visit 1).
- 4) Treatment for >14 days within the preceding month with >20 mg. prednisone (or equivalent) or any treatment during the last month with a cellular immunosuppressant (e.g., cyclophosphamide, methotrexate, calcineurin inhibitors, etc.), given increased risks of opportunistic infections.
- 5) Treatment with any investigational agent within 4 weeks of Screening (Visit 1) or 5 half-lives of the investigational medicinal product (whichever is longer).
- 6) Fertile women who do not agree to abstinence or an effective form of contraception (as approved by the investigator), or who are breast feeding, for 4 weeks before randomization until 90 days after the last administration of study medication (or placebo).
- 7) Men who are not surgically sterile and do not agree to remain abstinent from heterosexual intercourse or use effective contraception (as approved by the investigator), and refrain from donating sperm, from the time of giving informed consent until 90 days after the last administration of study medication (or placebo).
- 8) Subjects with known hypersensitivity to GKT137831 or its excipients (e.g. capsule "bulking" agents).
- 9) A history of bone marrow disorder including aplastic anemia, or marked anemia defined as hemoglobin < 10.0 g/dL (or 6.2 mmol/L).
- 10) Severe cardiovascular disease, defined as any of the following within the preceding 12 weeks: acute myocardial infarction or unstable angina, a coronary revascularization

procedure, congestive heart failure (NYHA Class III or IV), or stroke, including a transient ischemic attack.

- 11) Evidence of cardiac conducting abnormalities, defined as second or third degree AV block not successfully treated with a pacemaker, or a personal or family history of long QT syndrome (QTc interval >450 msec for males or 470 msec for females).
- 12) End-stage renal disease requiring dialysis.
- 13) Undergoing transplantation evaluation, or listed with the United Network for Organ Sharing (UNOS) as a lung transplantation candidate at the time of enrollment in this trial.
- 14) Liver function tests (transaminases, alkaline phosphatase, direct and total bilirubin) >3x upper limit of normal values.
- 15) Systemically administered potent CYP3A4 **inhibitors or inducers** are prohibited during the 24-week treatment period.

Inhibitors include: boceprevir, cobicistat, conivaptan, ritonavir, itraconazole, ketoconazole, telaprevir, troleandomycin, voriconazole, clarithromycin, diltiazem, idelalisib, nefazodone, nelfinavir.

Inducers include carbamazepine, enzalutamide, mitotane, phenytoin, rifampin.

See also: <https://www.fda.gov/drugs/drug-interactions-labeling/drug-development-and-drug-interactions-table-substrates-inhibitors-and-inducers#table3-2>

Subjects who fulfill all inclusion criteria and meet no exclusion criteria will be eligible for randomization.

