Major Exclusion Criteria:	
 1) Diagnosis of major comorbidities expected to interfere with study participation 2) History of malignancy within the last 5 years, excluding basal or squamous cell skin cancer and low-risk prostate cancer, the latter defined as stage T1 or T2a, with prostate specific antigen <10 ng/dl. NOX inhibition is not known to promote cancer, and these criteria are within current guidelines. 3) The occurrence of any acute infection requiring systemic antibiotic therapy within 2 weeks prior to Screening (Visit 1).

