PROTOCOL MODIFICATIONS made to Version 7.0 on April 5, 201 (to become Version 8.0)

- 1) The interval since original diagnosis of IPF has been changed from 5 years to 10 years
- 2). The exclusion for history of cancer has been modified to “within the last 5 years”.

INFORMED CONSENT MODIFICATIONS made on August 1, 2020 to now become ICF v4 08/01/2020.

- 1) The serial PFTs and 6MWD measures at 6, 12, and 18 weeks (see #2 above) have been deleted.

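### The PSA limit in the low-risk prostate cancer exception is given in ng/dL in all three places; 10 ng/dL is 0.1 ng/mL, so the unit needs confirming

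*Combined protocol and SAP*

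**What the plan says.** The malignancy exclusion appears three times in the current text.

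- **Section 2.3, Exclusion 2.** A history of malignancy excludes, with an exception for basal or squamous cell skin cancer and for "low-risk prostate cancer, the latter defined as stage T1 or T2a, with prostate specific antigen <10 ng/dL".
- **Synopsis, Major Exclusion Criteria 2.** The opening is narrower: "History of malignancy within the last 5 years, excluding basal or squamous cell skin cancer and low-risk prostate cancer". The prostate definition then continues "the latter defined as stage T1 or T2a, with prostate specific antigen <10 ng/dl".
- **Section 5.7.3.1.** The prostate definition and the PSA limit match the Synopsis, but the 5-year limit is absent, as it is in Section 2.3.

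The reason given for the criterion is that "NOX inhibition is not known to promote cancer, and these criteria are within current guidelines". No guideline is named and no guideline PSA value is reproduced. For Version 8.0 the amendment log (Section 10) records that "The exclusion for history of cancer has been modified to “within the last 5 years"; it does not mention the PSA limit. Section 2.3 closes by admitting to randomization only those who meet every inclusion criterion and no exclusion criterion, so the limit is operative.

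**The concern.** Laboratories usually report PSA in ng/mL. That is ordinary laboratory convention and is not stated in the protocol. A limit of 10 in ng/dL is 100 times stricter than a limit of 10 in ng/mL. The exception exists to keep men with early-stage, low-risk prostate cancer eligible, and the protocol justifies it by saying that the drug's mechanism is not known to promote cancer. A ceiling of 0.1 ng/mL is hard to square with that purpose.

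What is at stake is consistent eligibility across five centres. PSA is not among the screening tests in Section 2.6.2, so a site will take the value from outside records, in whatever unit the laboratory printed, and compare it with the protocol's number. One site may convert and another may not. As written, a man enrolled on the unconverted number is a protocol deviation. Section 5.6.1 adds that developing an exclusion criterion may be cause for stopping study drug, so the threshold could matter after randomization too. The group concerned is men, in a disease that Section 5.7.3.2 describes as mainly male and mainly of older people.

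**Working it through.** **Inputs.** PSA limit: below 10 ng/dL (Section 2.3; the same limit, written ng/dl, in the Synopsis and Section 5.7.3.1). Conversion: 1 dL = 100 mL. The plan derives no figure from this limit, so there is no calculation of its own to reproduce.

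**Step 1. Convert the limit.** x ng/dL = x / 100 ng/mL, so 10 ng/dL = 10 / 100 = 0.1 ng/mL.

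**Step 2. Convert the same number the other way.** 10 ng/mL = 10 × 100 = 1000 ng/dL. The ratio of the two readings is 1000 / 10 = 100.

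**Step 3. Apply each reading to the same man.** The PSA values below are illustrations, not data from the documents. Each man is assumed to have a T1 or T2a cancer that falls within the exclusion.

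| Reported PSA (ng/mL) | In ng/dL | Site converts units: below 10 ng/dL? | Site compares only numbers: below 10? |
|---|---|---|---|
| 0.05 | 5 | Yes, exempt | Yes, exempt |
| 0.1 | 10 | No, excluded | Yes, exempt |
| 4 | 400 | No, excluded | Yes, exempt |
| 12 | 1200 | No, excluded | No, excluded |

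The two readings disagree exactly where 0.1 ≤ PSA < 10 ng/mL. Below 0.1 both exempt; at 10 or above both exclude.

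**Step 4. Is the unit an isolated misprint or a PDF-reading fault?** All three copies agree. That makes a reading fault unlikely, and it also means that no copy shows a different intended unit.

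**Step 5. Who is reached?** Under the Synopsis wording, a cancer more than 5 years old does not exclude, so the PSA limit is irrelevant to that man. Under Sections 2.3 and 5.7.3.1, which set no look-back, it applies to a cancer of any age.

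**Step 6. How many men?** Section 3.1 expects about 40% women among eligible subjects, so about 60 × (1 − 0.40) = 36 men in the trial. Going from there to the number affected would need the share of male candidates with a qualifying prostate cancer and the distribution of their PSA values. The documents give neither. The 36 are also men who passed the criteria, so they are not the pool from which men are excluded. No count can be derived.

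**The case against.** The strongest reply is that the documents contain no contradiction about the unit. The three copies agree, no other section gives a PSA value, and the guideline is not named. That PSA is usually reported in ng/mL is common knowledge, but what limit was intended is an inference. This stands: the documents show an implausible unit, not a proven error, and they do not license a reviewer to choose the replacement.

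A reader might go further and infer that the exception is void for almost every man it was meant to admit, or that every man with a PSA from 0.1 to just under 10 ng/mL is misclassified. The documents do not support either.

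- The criterion concerns a history of cancer, so it includes treated men. It does not say whether the PSA is the value at diagnosis or the current one. If the current value counts (an assumption), men with a very low PSA after treatment could still qualify.
- Saying how many men are shut out needs a PSA distribution, which the documents lack.
- Calling the men in that range misclassified presumes that ng/mL was intended. In practice, a site that compares only the numbers would enrol them.
- The 5-year look-back in the Synopsis removes men with older cancers from the question.

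The reply does not remove the defect. The threshold decides eligibility, the literal reading fits poorly with the exception's purpose, and two sites acting in good faith can reach opposite decisions on the same man.

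**Conclusion.** The point holds as a probable unit error in an operative eligibility threshold. The factor of 100 is exact. The range on which sites can disagree, 0.1 to just under 10 ng/mL, follows directly from it, given that sites receive PSA results in ng/mL. That a slip occurred is a judgement. It rests on the usual reporting unit and on the poor fit between a 0.1 ng/mL ceiling and an exception for T1 or T2a disease.

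The number of candidates affected is unknown and probably small. The sample size, power, type I error and primary analysis do not depend on it. This is a low-priority correction, worth making because the criterion is applied at every site and the remedy is nearly free.

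**What to change.** The sponsor should check the PSA limit and its unit against the guideline it relies on, name that guideline, and correct the Synopsis, Section 2.3 and Section 5.7.3.1 together. It should also state whether the limit applies to the PSA at diagnosis or to the current value, since no PSA test is scheduled at screening. If the unit changes, sites should be told, and any eligibility decision already taken under this exception should be reviewed.

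The same edit should reconcile the 5-year look-back, which is in the Synopsis but not in the other two sections. That is a separate inconsistency, but it determines which men the PSA limit reaches.

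The cost is a wording change in three places and a short notice to sites, with no change to the design, sample size or analysis.
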